### 7.1.2. Subgroup Analyses

The primary endpoint described in Section 7.1.1 will be summarized using descriptive statistics by each subgroup listed below. No hypothesis testing will be performed in the subgroup analyses.

- Muscle location
- Steroid use
- Exon mutation location
- Visit 3 biopsy date (impacted by COVID-19 and not impacted by COVID-19)

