### 3.3. Sample Size Determination

Approximately, 15 to 20 ataluren-naïve male subjects, aged  $\geq 2$  and  $< 8$  years of age is planned to be enrolled in this study. Limited information is available about the magnitude and intra-subject variability of the change in dystrophin levels, as measured by an immunoassay such as ECL following 40 weeks ataluren therapy in this patient population. Assuming a baseline dystrophin level of 0.2% of control levels (as per previous dystrophin replacement therapy [Center for Drug Evaluation and research Application number: 206488Orig1s000 Eteplirsen Summary Review]), Table 1 shows the number of subjects needed to achieve an 85% power to detect an increase from baseline in dystrophin of 0.04%, 0.06% and 0.08%, for intra-subject coefficients of variability ranging from 20% to 35%, using a one-sided test at alpha 5%. As an example, if the increase from baseline is 0.08% and the intra-subject coefficient is 30%, 13 evaluable subjects would be required to have a power of 85% to detect this increase.

**Table 1: Summary of number of subjects required to achieve 85% power to detect increase in dystrophin levels from baseline**

Increase of dystrophin from baseline	Intra Subject CV			
	20%	25%	30%	35%
0.04%	19	29	41	55
0.06%	10	15	21	28
0.08%	7	10	13	18

**Abbreviations:** CV, coefficients of variability

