### 5. GENERAL CONSIDERATIONS

#### 5.1. Tables, Figures, and Listings

In general, continuous variables will be summarized using descriptive statistics including n (number of subjects), mean, standard deviation, median, minimum, and maximum. Categorical variables will be summarized using frequency count as number and percentage of subjects. Unless specified, all hypothesis testings are 1-sided at a 5% alpha level.

By subject data listings will be created for selected electronic case report form (CRF) domains sorted by subject and associated dates.

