### 7.1. Primary Efficacy Analyses

#### 7.1.1. Primary Analysis

The primary efficacy endpoint is the percent change from baseline in dystrophin levels (final concentration) following 40 weeks of ataluren therapy, as measured by ECL. The final concentration is calculated by dividing a sample's dystrophin concentration by its total protein concentration. In addition, the percentage of the predicted levels (% normal) will also be calculated as dystrophin levels normalized to dystrophin concentration of the control population ([Syneos Health Report No. 14597.051619.A](#)):

$$\% \text{ normal (in \%)} = 100 * \text{final concentration} / 33.8$$

Within each muscle location, the best, median, and the average of the dystrophin levels and the corresponding % normal values of the muscle cores will be summarized using descriptive statistics for each subject. In case any measured dystrophin concentrations are below the lower limit of quantification (LLOQ), the dystrophin concentrations will be set at 0.5\*LLOQ in the final concentration calculation for the statistical analysis.

The null hypothesis of the primary analysis is that the percent change from baseline in dystrophin levels following 40 weeks of ataluren therapy as measured by ECL is zero with the alternative hypothesis being that the change is greater than zero. To evaluate this hypothesis, a one-sided test at the 5% significance level will be employed.

The percent change from baseline at Week 40 in dystrophin levels measured by ECL will be analyzed using the mixed effect model repeated measurement (MMRM) analysis with factors of muscle locations, visits (baseline and Week 40) as fixed effects, and subjects as a random effect, based on ITT population. An unstructured covariance matrix will be used, and if the model fails to converge, then a compound symmetry matrix will be used. Since dystrophin level is known to be non-normally distributed, a log-transformation will be used in the analysis. The best dystrophin levels across all muscles are considered the primary analysis. A sample SAS code of the MMRM model is provided as follows:

```
proc mixed data = dataset;  
  
class subjid visit mlocation; /*mlocation is muscle location*/  
  
model lnaval = visit mlocation; /*lnaval is log-transformed dystrophin level*/  
  
random subjid;  
  
repeated visit / type = un;  
  
estimate "Week 40 change from baseline" visit -1 1;  
  
run;
```

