As supportive analyses, the average and median dystrophin levels across all muscles, and the subgroup analyses of the best, median, and mean dystrophin levels within each muscle location will be considered. In addition, the two-sided 90% confidence interval of percent change from baseline in dystrophin levels at Week 40 and the ratio (%) of dystrophin level at Week 40 versus baseline will also be provided.

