## 7.2. Secondary Efficacy Analyses

### 7.2.1. Secondary Efficacy Analysis

The secondary efficacy endpoint is the percent change from baseline in dystrophin levels (mean membrane stain density) after 40 weeks of ataluren therapy as determined by a validated IHC assay. Within each muscle location, the best, median, and the average dystrophin levels of the muscle cores will be summarized using descriptive statistics for each subject. The secondary efficacy endpoint will be analyzed using the same method as described in Section 7.1.1 (Primary Analysis). The best dystrophin levels across all muscles are considered the primary interest. As supportive analyses, the average and median dystrophin levels across all muscles, and subgroup analyses of the best, median, and mean dystrophin levels within each muscle location will be considered. In addition to dystrophin levels (the mean staining intensity), the percentage of positive fibers will also be summarized using descriptive statistics.

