### 7.2.2. Sensitivity Analyses

The following analyses will be considered as sensitivity analyses for the secondary efficacy endpoint:

- PP analysis: The same secondary efficacy analysis described in Section 7.2.1 (Secondary Analysis) will be repeated based on PP population for the secondary efficacy endpoint.
- The average and median dystrophin levels (mean membrane stain density) across all muscle locations will be analyzed using the same analysis method as described in Section 7.2.1 (Secondary Analysis).
- Excluding subjects with baseline dystrophin levels [REDACTED] of the predicted levels: The same analysis described in Section 7.2.1 (Secondary Analysis) will be repeated excluding subjects with baseline dystrophin levels [REDACTED] of the predicted levels. The same analysis on the average and median dystrophin levels across all muscle locations will also be repeated excluding such subjects.
- Subgroup analysis: The subgroup analysis by muscle location will be performed on secondary efficacy endpoint as described in Section 7.1.2 (Subgroup Analyses).
- COVID-19 considerations: The Week 40 study day (defined as Week 40 biopsy date – first study drug date +1) will be added to the efficacy analysis model described in Section 7.2.1 (Secondary Analysis) as a covariate. This analysis model will be applied to the best, average, and median dystrophin levels analyses based on the ITT population.

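### Do the subgroup tables in SAP 7.1.2 need a geometric Week 40/baseline ratio because the primary model is on the log scale?

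*SAP*

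**What the plan says.** SAP 7.1.2 covers four subgroup factors: muscle location, steroid use, exon location, and whether COVID-19 affected the Visit 3 biopsy date. Its rule is: "The primary endpoint described in Section 7.1.1 will be summarized using descriptive statistics by each subgroup listed below". It rules out hypothesis tests in these tables and names no particular statistic. The statistics come from SAP 5.1, which asks for "descriptive statistics including n (number of subjects), mean, standard deviation, median, minimum, and maximum". The word *including* leaves that list open.

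The endpoint being summarized is the percent change from baseline in ECL dystrophin. SAP 7.1.1 gives the reason for the model's scale: "Since dystrophin level is known to be non-normally distributed, a log-transformation will be used in the analysis". Among the results of that section, "the ratio (%) of dystrophin level at Week 40 versus baseline will also be provided", with a two-sided 90% interval for the percent change. For muscle location, SAP 7.1.1 also plans supportive within-muscle analyses, and SAP 7.2.1 does the same for IHC: "subgroup analyses of the best, median, and mean dystrophin levels within each muscle location will be considered".

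Biopsy timing is also taken up elsewhere. SAP 4.4 removes boys whose Week 40 visit falls outside 38 to 42 weeks from the per-protocol set. SAP 7.1.3 repeats the log-scale primary model on that set and, separately, adds the biopsy study day to the model as a covariate.

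**The concern.** The model and the subgroup tables appear to use different yardsticks. A log-scale model back-transforms to a geometric mean ratio. An arithmetic mean of individual percent changes is a different quantity and is always at least as large as the geometric mean ratio minus 1 in the same boys. For steroid use, exon location and COVID-19 impact, the SAP lists no geometric ratio, although SAP 9 names a geometric mean for plasma concentrations.

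In a single-arm study there is no control group to show up such a tilt. A reader who sets a subgroup mean beside the model ratio could take the difference for a subgroup effect, or see an increase where there is none. With no drug effect and eight boys, the mean percent change would be positive in 63% to 72% of samples rather than half.

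**Working it through.** **Inputs.** SAP 3.3: baseline 0.2% of control; increases of 0.04, 0.06 and 0.08 points (ratios 1.2, 1.3, 1.4); intra-subject CV 20% to 35%; one-sided 5%; 85% power. SAP 5.6: 8 boys with a late Visit 3. With 15 to 20 enrolled, the other COVID-19 group has 15 − 8 = 7 to 20 − 8 = 12 boys.

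**1. Reproduce the plan's figure.** Take a paired t-test on the log ratio with effect ln(1 + increase/0.2) and SD √2 × CV. For an increase of 0.08 and CV 30%, the effect is ln 1.4 = 0.336 and the SD is 0.424, giving n = 13 as in SAP Table 1. Eleven of the 12 cells match; the other is 27 against 28. The planning is therefore consistent with a log-ratio model, although the SAP does not state one.

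**2. Size of the tilt.** With log-normal levels and independent errors at the two visits, the log ratio has variance 2CV². The expected arithmetic mean percent change is R·exp(CV²) − 1, where R is the true ratio:

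| CV | R = 1.0 | R = 1.2 |
|---|---|---|
| 20% | +4.1% | +24.9% |
| 25% | +6.4% | +27.7% |
| 30% | +9.4% | +31.3% |
| 35% | +13.0% | +35.6% |

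So the tilt exists.

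**3. Does it separate one subgroup from another?** The expression in step 2 does not contain n. Two subgroups with the same R and CV have the same expected mean percent change. The average gap between the arithmetic and geometric summaries in the same n boys, with no effect, is exp(CV²) − exp(CV²/n):

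| n | CV 20% | CV 35% |
|---|---|---|
| 7 | 3.5 points | 11.3 points |
| 8 | 3.6 points | 11.5 points |
| 12 | 3.7 points | 12.0 points |

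For the two COVID-19 groups (8 against 7 to 12), the gaps differ by about 0.5 point at most.

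**4. Compare it with the noise.** At n = 8 with no effect, the sampling SD of the mean percent change is 10.6 points (CV 20%) to 21.1 points (CV 35%). The gap is 3.6/10.6 = 0.34 to 11.5/21.1 = 0.55 of that SD.

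**5. What the planned median gives.** Percent change is a monotone function of the log ratio, so under log-normality the population median percent change equals R − 1, which is also the target of the model ratio. Simulated averages at n = 8 with no effect:

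| Summary | Average, CV 20% to 35% | Sampling SD |
|---|---|---|
| Median | +0.8% to +2.6% | 11.7 to 21.1 points |
| Geometric ratio − 1 | +0.5% to +1.5% | 10.1 to 17.9 points |

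Adding the geometric row would remove about 1 point of tilt or less beyond what the median already removes, with a sampling SD about 14% to 15% smaller.

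**The case for a change.** The best case for a change is that the inequality is mathematical and does not depend on the assumptions; only its size does. At CV 35% the tilt of 13.0 points is more than half the smallest planned effect of 20% (0.04 on 0.2). The median is no complete substitute: it is noisier, and in a cell of two boys, likely for exon location, it equals the arithmetic mean. One extra row would cost almost nothing.

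All of that is correct, but none of it shows that following the SAP misleads. In cells of one or two boys no summary carries much information, and at n = 1 the arithmetic and geometric versions coincide.

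The equal-tilt argument does need a common CV. If one group of eight had CV 20% and another CV 35%, their expected means would differ by 13.0 − 4.1, about 9 points, with no effect. The sampling SD of that difference is √(10.6² + 21.1²) = 23.6 points, and the medians beside them would differ by only 2.6 − 0.8, under 2 points, on average.

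For COVID-19, the per-protocol repeat in SAP 7.1.3 gives a log-scale result largely in boys biopsied on time, and the biopsy-day covariate looks at timing on the same scale. Neither is a ratio for each COVID-19 group, so this point only supports the conclusion; it does not settle it.

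**Conclusion.** The concern does not hold. The mean percent change is a valid summary of the endpoint as named, the median beside it tracks the model's quantity closely, and the open list in SAP 5.1 allows a geometric ratio if the sponsor wants one. The tables are descriptive and untested, and no decision rests on them. The primary test, its interval, the overall ratio and the sample size are the same either way. What remains is a difference of scale between a subgroup mean and the overall model ratio, expected at 4 to 13 points with no effect and below sampling error in the group of eight.

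These sizes assume log-normal levels, independent visit errors and the planning CVs. The SAP itself cautions: "Limited information is available about the magnitude and intra-subject variability of the change in dystrophin levels, as measured by an immunoassay such as ECL". A CV of 10% would give a tilt of about 1% and a CV of 50% about 28%. The calculation does not model the half-LLOQ substitution or the use of the best value among several cores. No CV is given for IHC, so no size is claimed there. The conclusion does not depend on the exact size, because it rests on the descriptive role of the tables and on the median already being planned.

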### 7.1.3. Sensitivity Analyses

The following analyses will be considered as sensitivity analyses:

- PP analysis: The same primary efficacy analysis described in Section 7.1.1 (Primary Analysis) will be repeated based on the PP population for the primary efficacy endpoint.
- The average and median dystrophin levels across all muscle locations based on the same method as described in Section 7.1.1 (Primary Analysis).
- Excluding subjects with baseline dystrophin levels [REDACTED] of the predicted levels: The same primary analysis described in Section 7.1.1 (Primary Analysis) will be repeated excluding subjects with baseline dystrophin levels [REDACTED] of the predicted levels. The same analysis on the average and median dystrophin levels across all muscle locations will also be repeated excluding such subjects.
- COVID-19 consideration: The Week 40 biopsy study day (defined as Week 40 biopsy date – first study drug date +1) will be added to the primary efficacy analysis model described in Section 7.1.1 (Primary Analysis) as a covariate. This analysis model will

be applied to the best, average, and median dystrophin levels analyses based on the ITT population.

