### 4.3. Intent-to-Treat Population

This analysis set will include all enrolled subjects with treatment assignments. In addition, subjects in this analysis set must have a valid assessment of dystrophin levels at baseline, as measured by ECL. This analysis set will be used for the primary endpoint analyses and summaries of other efficacy endpoints.

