#### 5.3. Missing Data Handling

Unless specified, observed data will be used for all analyses. Missing data will not be imputed.

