#### **5.6. COVID-19 Related Considerations**

Due to the Coronavirus Disease of 2019 (COVID-19) pandemic, 8 subjects will have Visit 3 (Week 40 visit) later than planned due to closure of the study site to study procedures. These subjects will receive continued therapy with ataluren until final study biopsies can be obtained. Since many subjects will have their Week 40 biopsy performed much later than after 40 weeks of ataluren treatment therapy, a sensitivity analysis will be conducted to include the Week 40 biopsy study day as a covariate in the analysis model. This sensitivity analysis will be performed for both the primary and secondary efficacy endpoints as detailed in Section 7.1.3 (Sensitivity Analyses) for the primary efficacy endpoint and in Section 7.2.2 (Sensitivity Analyses) for the secondary efficacy endpoint.

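### The COVID-19 sensitivity model cannot adjust for late biopsies: biopsy day enters only as a main effect and cancels from the visit contrast

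*SAP*

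**What the plan says.** SAP 5.6 reports that site closure will make 8 Week 40 biopsies late, with ataluren continued until they can be done, and answers that "a sensitivity analysis will be conducted to include the Week 40 biopsy study day as a covariate in the analysis model". SAP 7.1.3 defines that day as biopsy date minus first-dose date plus 1 and says it "will be added to the primary efficacy analysis model described in Section 7.1.1 (Primary Analysis) as a covariate". This applies to the best, average and median levels in the ITT set. SAP 7.2.2 does the same for IHC: the day "will be added to the efficacy analysis model described in Section 7.2.1 (Secondary Analysis) as a covariate".

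The model being extended is in SAP 7.1.1. Its sample code has "model lnaval = visit mlocation; /*lnaval is log-transformed dystrophin level", a random subject effect, and "repeated visit / type = un" with no SUBJECT= option. The estimate is the visit contrast with coefficients −1 and 1. On covariance the text adds that "if the model fails to converge, then a compound symmetry matrix will be used".

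Two other rules matter. SAP 5.3 says "observed data will be used for all analyses. Missing data will not be imputed". SAP 4.3 says "subjects in this analysis set must have a valid assessment of dystrophin levels at baseline, as measured by ECL", so ITT membership requires neither a Week 40 biopsy nor a baseline IHC value.

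No section gives code for the sensitivity model, a visit-by-day term, a centring point or a revised contrast.

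**The concern.** The covariate takes the same value on a child's baseline row and Week 40 row. Its coefficient can explain why some children have higher levels at both visits. It cannot explain why the change between visits is larger in children biopsied later, and that is the question the delay raises.

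Section 5.6 offers this analysis as the answer to late biopsies in 8 of 15 to 20 children, that is 40% to 53% of the planned sample. If it returns the primary result by construction, agreement between the two will look like robustness and carry no information. The problem applies to both assays and to all three summaries (best, average, median).

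**Working it through.** **Inputs from the documents.** 15 to 20 children and intra-subject CV of 20 to 35% (SAP 3.3); 8 late biopsies (SAP 5.6); Week 40 target day 280 (SAP Table 2; 40 × 7 = 280); two-sided 90% CI (SAP 7.1.1).

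**Assumed.** 18 children, delay lengths, growth of dystrophin with extra treatment, variance components, and covariance within child, since SUBJECT= is not given.

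**1. The plan's own figure, to set the scale.** For an increase from 0.20% to 0.28% the log effect is ln(1.4) = 0.336. With CV 30% the SD of a log change is √2 × 0.30 = 0.424. A one-sided 5% paired t-test with 85% power needs 13 children, as SAP 3.3 states; all 12 cells of its table reproduce within 1. A log-change SD of 0.42 therefore matches the plan's 30% column.

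**2. Algebra.** For child i with biopsy day d:

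- baseline: y1 = a + c·d + u + e1
- Week 40: y2 = a + b + c·d + u + e2
- change: D = y2 − y1 = b + (e2 − e1)

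The term c·d is gone. The likelihood factorises into D ~ N(b, sD²) and y1 given D ~ N(a′ + c·d + g·D, s²). Only the first factor contains b and sD, so the estimate of b is mean(D), and neither it nor its SE depends on c. Compound symmetry gives the same result.

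**3. Numerical check by REML, complete pairs.** Visit contrast on the log scale (SE where available):

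| Simulated data set | Primary | Day as main effect | Visit-by-(day − 280) added |
|---|---|---|---|
| A, random subject, two muscles | 0.2957 (0.0622) | 0.2957 (0.0622) | 0.1971 (0.0794) |
| A, unstructured, best value | 0.2729 (0.0678) | 0.2729 (0.0678) | 0.1711 (0.0827) |
| B | 0.075265 (0.107659) | 0.075265 (0.107659) | −0.119443 (0.120448) |
| C | 0.149795 (0.109530) | 0.149795 (0.109530) | 0.014002 |
| D | 0.209960 (0.069119) | 0.209960 (0.069119) | 0.210408 |

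B to D show the range. The shift in B (−0.195) exceeds the average shift in every setting of step 6 and is not typical.

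Largest differences between the primary and main-effect models:

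- unstructured, 40 data sets: 1e-15 (contrast), 1.3e-8 (SE)
- compound symmetry, 40 data sets: 1.2e-15, 7.8e-9
- two muscle rows per visit, 10 data sets: 7e-16, 3.1e-9

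**4. Bias left in place.** Zero true change at day 280, log change rising 0.002 per day of delay, 8 of 18 children late by 45 to 199 days, 400 data sets. The mean primary contrast is 0.112 (ratio 1.12). The main-effect model matched the primary within 2e-16 in the 40 data sets fitted both ways. The centred interaction model averages 0.004 (ratio 1.00).

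**5. When the main-effect model does move.**

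- 2 of 18 Week 40 biopsies missing: those children have no covariate value, so their baseline rows drop out. The contrast moved by a median of 0.004 (max 0.048) and equalled the mean log change of the 16 remaining pairs to 2e-15.
- Best-value location differs between visits (30% of children, location effect 0.2): median 0.001, max 0.023.
- 2 of 18 baseline values missing, possible for IHC: median 0.001, max 0.021 with no growth; median 0.005, max 0.082 with 30% growth per 100 days. The mean shift was near 0.

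None of these is adjustment for delay.

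**6. Size, all inputs assumed.** 18 children, 8 late by 60 to 240 days (mean 150), SD 0.42. The expected excess in the unadjusted contrast is (8/18) × (150/100) × ln(1 + growth per 100 days). For 10% growth this is 0.667 × 0.0953 = 0.064; for 30%, 0.667 × 0.2624 = 0.175. In simulation the interaction term moved the estimate by 0, −0.064, −0.121 and −0.175 on average for growth of 0, 10, 20 and 30%. The main-effect covariate moved it by 0 throughout.

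**The case against.** The strongest objection is that the model is inferred. No code is given for the sensitivity analysis, the sample code lacks SUBJECT=, and calling the day a covariate does not strictly rule out an interaction. Section 7.1.1 also describes percent change as what is analysed, and with one change score per child as response, biopsy day would be informative. This stands as a statement that the text is underspecified. It does not rescue the plan: the visit factor and the sample code put log level at both visits on the left-hand side, and no section mentions an interaction. If something else was meant, the wording still has to change.

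Second, delay is partly covered elsewhere. The per-protocol set (SAP 4.4) excludes Week 40 visits outside 38 to 42 weeks, and SAP 7.1.2 splits ECL results by COVID-19 impact. At day 280 the interaction model is only a little more precise than a per-protocol analysis (mean 90% CI half-width 0.220 against 0.237 log units in the illustration), and it pays for that with a linearity assumption. That is fair. But the per-protocol set also excludes on compliance and baseline level, the split is descriptive, and SAP 7.2.2 carries over only the muscle-location subgroup for IHC. None of these estimates how the change varies with delay.

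Third, in a single arm a delay slope cannot separate longer exposure from age or disease progression. This stands and should be stated with the result.

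Finally, this is one sensitivity analysis among several, and the SAP does not say that an unchanged result will be cited as robustness. That limits the consequence; it does not give the analysis content.

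**Conclusion.** The concern holds. Read plainly, with a main effect only and covariance within child, the planned analysis reproduces the primary estimate and SE exactly for complete, location-balanced pairs. That follows from the algebra and depends on no assumed delay, growth, SD or test level. With incomplete or location-unbalanced data the estimate can move slightly, and the movement could be mistaken for adjustment.

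The size of the uncorrected effect does rest on assumptions: 0.064 to 0.175 log units (ratio inflated by a factor of 1.07 to 1.19) for growth of 10 to 30% per 100 days, and nothing if the effect does not grow with delay. The documents give neither the delays nor the growth. The primary inference is untouched. The text should be corrected because, as written, this analysis cannot answer the question put to it.

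**What to change.** In SAP 5.6, 7.1.3 and 7.2.2, define day280 = biopsy study day − 280, keep it as a main effect, and add its interaction with visit. State the within-child covariance through SUBJECT=. Report the visit contrast at day 280 and the interaction slope, each with a CI, beside the per-protocol result. For complete pairs this equals regressing each child's log change on (day − 280) and reporting intercept and slope.

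Centring is essential. With uncentred day, the existing contrast extrapolates to day 0; in data set A that gave −0.290 (SE 0.310) instead of 0.197 (SE 0.079).

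State that the analysis assumes a linear effect of delay, relies on children with a Week 40 biopsy, and cannot separate exposure from age or progression. Do not cite a main-effect model as evidence of robustness to delay.

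Cost: one model term and a few sentences of SAP text, with no new data. One residual degree of freedom for the change is lost (17 to 16 with 18 pairs). In the illustration the mean 90% CI half-width is 0.220 log units at day 280, against 0.170 to 0.192 for the primary analysis (growth 0 to 30%). The interval is usually, not always, wider: it was narrower in 0.2% to 26% of simulated trials across the main settings, and in 42% with delays of 90 to 360 days and 30% growth. The slope may be imprecise, with a half-width of about 0.21 per 100 days for delays of 60 to 240 days and about 0.53 for 30 to 90 days. These widths use the 90% level of SAP 7.1.1 and would grow if the CI followed the stricter test level in SAP 10.
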